13.2. Secondary Outcome Measures

- **Rate of recruitment of participants into trial:** The recruitment rate will be assessed on a monthly basis until the enrollment target is reached. The recruitment rate is operationalized as the total number of participants consented in one month. The per-month proportion of consented participants reaching the pharmacy follow-up phase will also be calculated, as well as the per-month proportion of pre-screened participants that were consented. These rates will be used to estimate the speed at which a future multi-site RCT could consent, enroll, and randomize participants.
- **Treatment retention in follow-up assessments:** Retention in follow-up assessments is defined as the proportion of study assessments completed (three follow-up assessments).
- **Opioid and other substance use:** The prevalence and frequency of opioid/heroin use and other substance use over the study duration will be examined.
- **Satisfaction of participants, physicians, and pharmacists with OUD care**

Satisfaction with treatment delivery by participants will be measured using the Treatment Satisfaction Survey (adapted from Harland et al., 2005) at each visit. The proportion of visits in which participants are satisfied (score of 4 on a Likert Scale of 1-5) or very satisfied (score of 5 on a Likert Scale of 1-5) will be calculated. Pharmacist and physician satisfaction with treatment delivery will be measured using the Treatment Satisfaction Survey on a monthly basis, and a proportion of physician and pharmacist monthly ratings of satisfied or very satisfied will be calculated.

- **Participant safety, as measured by:**

- a) Any fatal or non-fatal substance use-related overdose measured by self-report.
- b) Any substance use-related ED visit or hospitalization measured by self-report.

13.3. Statistical plan and data analysis.

This is a feasibility study, and as such there are no a priori hypotheses. The main objective is to understand the feasibility regarding the study design features and operational procedures in order to inform the design of a full scale clinical trial (e.g., whether participants can be recruited in a timely fashion, whether the collaboration between the OTP and pharmacist can ensure standard methadone treatment for Opioid Use Disorder).

Because this is a non-randomized pilot study with a small sample size, descriptive analyses will be conducted to describe distributions of primary and secondary outcome measures. Generalized estimating equation (GEE) models will be considered and used to assess outcomes that are measured repeatedly throughout the study follow-up phase.

14. Early stopping rules.

The study may be modified, suspended, or terminated at the recommendation of the Study PI or the Duke IRB. This might occur if the community pharmacy experiences unexpected difficulties in administering and/or dispensing methadone. At the very least, new enrollment in the study would likely be suspended until this unanticipated outcome was fully reviewed by the investigator team and the Duke IRB, in consultation with the NIDA Program Official (as needed).

15. Risks

15.1. Medical risks, listing all procedures, their major and minor risks and expected frequency.

This small pilot study will recruit clinically stable and well-functioning patients that receive up to 13 take-home methadone doses at one time. Medical risk as well as the methadone diversion risks are low.

15.2. Steps taken to minimize the medical and diversion risks.

(1.) As mentioned in the section 4.3, this study includes **several safety assessments** to collect the safety information or indicators from each participant monthly in order to identify and address safety issues timely. Safety assessments include Patient Health Questionnaire (PHQ-9, depression screen), P4 Screener (suicide risk screen), Pregnancy and Birth Control Assessment, and Safety Event Response Checklist.

As methadone is an approved medication being prescribed in accordance with the approved usage, there would be no need to capture Adverse Events (AEs) per se, as the likely AEs are already known. However, in terms of compliance, informing dosing, side effects or monitoring those aspects, a solicited collection of information is relevant. To aid the collection of safety events, a tool in the form of a Safety Event Response Checklist with solicited symptom information, yes/no responses, and level of severity (mild, moderate, severe) will be developed. The checklist will be used by research staff to obtain self-reported information from each participant at each monthly research visit. The data will be captured electronically in the database. The Manual of Operating Procedures (MOP) will specify the process of reporting safety events that may require interventions (such as dosing, side effects, etc.) to study physician (Site PI) and pharmacists, as well as to Study PI.

- ✚ For the purposes of this protocol, the following safety events will be collected and reported to inform dosing as well as assist with monitoring of methadone compliance. Side effects of the medication

may include but are not limited to: headache, nausea, vomiting, constipation, excessive sleeping/insomnia, excessive sweating, pain, swelling, and overdoses.

(2.) In addition, we will collect all Emergency Department (ED) visits, hospitalizations, overdose, and death of any participant who provided written informed consent.

- ✚ Non-fatal overdoses since the last visit will be captured via self-report using the Safety Event Response Checklist at the Intake/Baseline and each monthly research visit following consent (or the Early Termination Visit participant discontinues study participation early). Research staff will report overdose events to PI and Site PI ([name]) to terminate the participant from the study and return the participant to the OTP for medication administration, change in take home regimen, and other appropriate intervention.
- ✚ Data on fatal overdoses may be collected via medical chart record review, if medical records data is available, at Visit 4 (or the Early Termination Visit if the participant discontinues study participation early). This will be supplemented with information from contacts with persons listed on the participant's locator form when participants are lost to follow-up throughout the study. Fatal overdoses will be captured on the Safety Event Response Checklist.
- ✚ All deaths, regardless of cause, will be captured for this study. These events will be identified through the participants' locator information, or when possible through using state medical examiner records, National Death Index, and/or review of medical records. Deaths will be reported using the Safety Event Response Checklist.

(3.) Urine drug screens (UDS) will be collected by the OTP clinic at Intake/Baseline, at each monthly research visit (1 month, 2 months, and 3 months following study intake), and/or as needed based on clinical decision.

- ✚ In this study, UDS results demonstrating ongoing opioid use or other illicit/nonmedical substance use (e.g., cocaine) will be reported to the site PI to determine whether the participant should continue in the study.
- ✚ If illicit or non-prescribed opioid use is reported, found on drug testing, or suspected at any time during treatment, the participant will be contacted to perform at least one random UDS (as needed) prior to the next scheduled visit and referred to the study physician for an assessment and to determine whether the participant should continue in the study.
- ✚ Any non-prescribed use of benzodiazepines that is detected will prompt analogue measures to those adopted for opioid use. The abuse of other substances or alcohol will result in early termination from the study and return to the OTP for methadone dosing and possible adjustment of the take home schedule.

(4.) Measures of adherence will be monitored and assessed, including: (1) adherence to scheduled pharmacy visits for dose administration and take-home pickup and (2) success in methadone call-back (e.g., failed methadone dose call back as an indicator treatment non-adherence). Failure to attend the random methadone dose call-back visit will be considered as an indicator of non-adherence.

- ✚ If the participant fails to return to the pharmacy for the random methadone call back visit during the study or any tampering/diversion is suspected, the participant will be discontinued from the study and returned to the OTP for methadone dosing and adjustment of their take home schedule as determined by the OTP provider.
- ✚ If the participant misses two consecutive visits, he/she will be discontinued from study and contacted by pharmacist/research staff to complete the Early Termination Visit and be referred back to the OTP clinic.

15.3. Plan for reporting unanticipated problems or study deviations.

All protocol-defined safety events (medical and/or psychiatric) occurring during the course of the study will be assessed, documented, and reported. Safety events occurring during the course of the clinical trial will be collected, documented, and reported by the PI and/or site PI according to the Manual of Operating Procedures. Appropriately qualified and trained personnel will elicit participant reporting of safety events at each study visit designated to collect safety events (i.e., the first visit following informed consent and at every study visit thereafter).

A study Medical Monitor ([name]) will review or provide consultation for each safety event as necessary. The study Medical Monitor, study PI, and site PI will also make decisions to exclude, refer, or withdraw participants as required. The study staff will be trained to monitor for and report safety events. Individuals who experience a safety event that compromises safe participation in the study will be discontinued from further medication administration and provided referrals for other treatment or to specialized care. Study personnel will request that the participant complete an Early Termination Visit to assure safety and to document end-of-intervention outcomes.

- ✚ Serious adverse events (SAEs) will be reviewed by study Medical Monitor and discussed with PI, Site PI and other investigators, and reported to the Duke IRB based on the current Duke IRB policy:
 - Immediately (within 24 hours) upon learning of an unanticipated study-related death, study personnel will notify the IRB via phone or email by providing a brief summary of the event. Then within 1 week (5 business days), study personnel will send to the Duke IRB a Safety Event submission.
 - For a reportable serious adverse event, study personnel will notify the IRB within five (5) business days of the investigator becoming aware of the event. Study personnel will send a Safety Event submission to the Duke IRB.
 - For any other problem or event requiring prompt reporting to the Duke IRB, within ten (10) business days of the investigator becoming aware of the event, study personnel will send to the Duke IRB a Safety Event submission.
- ✚ For the purposes of this study, any attempts to divert methadone will be recorded as an SAE and reported according to the above guidelines). Study PI ([name]) is responsible for informing NIDA of any actions taken by the Duke IRB as a result of its regular reviews of the project.
- ✚ Study PI will inform the NIDA Program Official immediately of any major change in the protocol or its status, such as suspension or termination of subject recruitment or of the protocol itself; changes in the informed consent or IRB approval status; and other problems or issues that could have a significant impact on participants. All changes to the protocol must be approved by the Duke IRB prior to implementation.

15.4. Legal risks such as the risks that would be associated with breach of confidentiality.

There is the potential for breaches in participant confidentiality. Whenever sensitive personal information is handled, there is a small risk of an accidental or intentional breach of confidentiality. To protect the confidentiality of study participants, all information collected as part of this study will be maintained in locked cabinets and/or secured project folders approved by Duke IRB. Research staff with access to this information must have completed IRB required training and study supervision in the protection of research confidentiality. No individually identifiable information will be released without prior and proper written authorization from study participants. All study staff will be trained in the rules and procedures of confidentiality and of the possibility of personal legal liability, should a breach of confidentiality occur.

15.5. Financial risks to the participants.

There are no financial risks to the participants.

16. Benefits

Description of the probable benefits for the participant and for society.

Study participants may enjoy the convenience of receiving methadone dosing at the community pharmacy, a setting which has longer daily hours of operation than the OTP clinic. Data from this study will be used to support further study of using community pharmacies to extend access of methadone treatment services to patients in both urban, and perhaps most important, rural areas.

17. Payment and Remuneration

Detail compensation for participants including possible total compensation, proposed bonus, and any proposed reductions or penalties for not completing the protocol.

Pilot trial: Each participant will be compensated for their time and transportation for the baseline assessment (\$50) and the 3 follow-up research assessments (\$50/each). Participants who sign the informed consent but they are found to be a screen failure (i.e., not meeting all inclusion criteria) will be compensated for \$10 for their time.

Qualitative interviews following the pilot trial: Follow the completion of the pilot trial, qualitative interview will be conducted with study participants, pharmacists/staff, and OTP providers/staff to better understand barriers and facilitators of pharmacist dispensing methadone for opioid use disorder. Each participant will be compensated \$50 for their time for participating in the qualitative interview.

18. Costs

Detail costs of study procedure(s) or drug (s) or substance(s) to participants and identify who will pay for them.

There will be no charge to study participants for receiving their methadone administration and dispensing through the pharmacy during the study. These costs of methadone medication dispensed at the pharmacy for the study will be paid by research funds from the National Institute on Drug Abuse, the National Institutes of Health (NIH).

REFERENCES

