The operation for the pharmacy administration and dispensing of methadone for OUD treatment will be based on the available treatment guidelines for pharmacy-based medication management and Medication-assisted treatment (MAT) for OUD, including SAMHSA's guidelines to the federal OTP regulations and the guideline for pharmacy-based supervision of methadone consumption from other countries (Adams et al., 2015; Hill, 2014; Ontario Pharmacists Association, 2017; SAMHSA, 2015a, 2015b; SAMHSA, 2018a;). An Operational Care Agreement (OCA) will be used to define the respective roles of the methadone medical provider (supervising care and writing prescriptions) and pharmacist and determine study procedures. The OTP will continue to follow routine care practices and procedures as usual during the study and provide counseling, medical supervision, and urine drug testing. The study pharmacist will administer and dispense methadone according to the OTP provider's prescription.

Participants will be assessed at baseline (following informed consent). Outcome assessments will be conducted at each monthly visit throughout the follow-up phase of the study. Assessments will focus mainly on the feasibility and acceptability of pharmacy-based methadone administration and dispensing in order to inform the development of a future multisite randomized clinical trial. **Primary outcome** will be medication adherence. Measures of adherence will include: (1) adherence to scheduled pharmacy visits for dose administration and take-home pickup and (2) success in methadone call-back (e.g., failed methadone dose call back as an indicator treatment non-adherence). **Secondary outcomes** will include recruitment rate, treatment retention, opioid and other substance use, participant treatment satisfaction, pharmacist and physician treatment satisfaction, and participant safety. Information generated from this pilot study will inform the development of a future randomized controlled trial, which will test the effect of pharmacy-OTP collaborative care model for the management of patients with OUD.

2. Objectives

The overarching goal is to explore the feasibility and acceptability of transferring methadone dose administration and take-home methadone dispensing for OUD treatment for stable patients from OTPs to pharmacies. We will achieve this goal by pursuing the following primary pilot study objectives.

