- a) Calculate the rate of recruitment, defined as the number of participants enrolled in the study out of the number of MMT patients who are potentially eligible and approached for participation. The average monthly rate of participants starting pharmacy-based methadone dispensing for OUD among enrolled participants will also be calculated. The number of potential participants pre-screened and the reasons for pre-screen failure and screen failure will also be evaluated.
- b) Calculate the adherence to methadone treatment defined as (1) the proportion of methadone take-home doses dispensed at the pharmacy out of the total number of take home doses prescribed and (2) the proportion of successful scheduled methadone dose call-back with no signs of methadone diversion.
- c) Examine retention in treatment, as determined by the proportion of participants who remain in treatment at the pharmacy during the 3-month follow-up phase.

- d) Examine the proportion of positive urine drug screens (UDS) over the study duration.
- e) Examine the number of days of self-reported substance use (alcohol intoxication, and other drugs) as collected on Timeline Followback (TLFB) over the study duration (Sobell, 1992; Sobell & Sobell, 2000).
- f) Determine indicators of participant satisfaction with treatment delivery measured using the Treatment Satisfaction Survey (adapted from Harland et al., 2005) obtained at each assessment; proportion of visits in which raters are satisfied (score of 4 on a Likert Scale of 1-5) or very satisfied (score of 5 on a Likert Scale of 1-5).
- g) Determine pharmacist and physician satisfaction with treatment delivery measured using the Treatment Satisfaction Survey at follow-up assessment, and a proportion of physician and pharmacist ratings of satisfied or very satisfied.
- h) Examine participant safety, as measured by: (1) Any fatal or non-fatal substance-related overdose measured by medical examiner record or self-report, respectively; and (2) Any substance-related emergency department (ED) visit or hospitalization, measured by self-report.

3. Background and rationale

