Participants will complete three follow-up assessments at 1-month, 2-months, and 3-months following the baseline visit. These follow-up assessments will be completed either in-person between the participant and research staff or remotely via phone or a Duke-approved teleconferencing platform for research. Assessments will focus on collecting clinical and safety information since the previous assessment, including substance use data via urine toxicology samples and self-report using the timeline followback (TLFB) assessment, compliance with psychosocial interventions, medication side effects or other safety events, and suicidality risk evaluation. The full list of assessments to be administered is included below (**Table 1**). Based on the convenience of the patient's time and methadone take-home schedule, monthly research assessment may be scheduled to occur on a day that take-home doses are scheduled to be dispensed. Completion of the intake/baseline assessments will take approximately 45-60 minutes. Follow-up research interviews will be briefer, about 30 minutes in duration.

Using the guidance from the pharmacy practice's collaborative practice agreements (CPAs), the role and responsibilities of study pharmacists (Health Park Pharmacy, Raleigh, NC) and study OTP prescriber/physician ([name]), including communication procedures, will be specified by an Operational Care Agreement (OCA) and signed by study pharmacists and [name]. Throughout the study, participants will continue to receive their usual care at the OTP (e.g., counseling, methadone provider

oversight of dose orders, urine drug screen) and participants will return to their OTP at the end of the study (i.e., 3 months after baseline). The last monthly study assessment (3 months after baseline) will occur remotely (via phone or a Duke-approved teleconferencing platform), at the OTP, or at the pharmacy; however, no methadone will be dispensed at the pharmacy as part of the 3-month assessment.

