Medical History and Charlson Comorbidity Index forms: Medical History form and Charlson Comorbidity Index form will obtain a medical and psychiatric history from the participant covering past and present health conditions to help determine eligibility and to provide baseline information (Austin et al., 2015). These data will be collected during screening only.

Psychosocial Counseling Attendance Form: Participants' psychosocial counseling attendance will be assessed at each visit (Intake/Baseline Visit and follow-up visits 2 through 4, or the Early Termination Visit if participant discontinues study participation early). It serves the purpose of monitoring and reporting whether counseling attendance matches what is recommended in the treatment plan at each visit. This will be accomplished through the data from the OTP records.

Concomitant Medications: Concomitant medications will be collected on the Concomitant Medications form at the Intake/Baseline Visit (Visit 1). Concomitant medications will be reviewed at every subsequent study visits (including Visit 4, or the Early Termination Visit if the participant discontinues study participation early), and changes will be documented on the form. The study medical clinician may exclude any participant taking medications that could interact adversely with methadone at his/her clinical discretion.

Study Completion: This form tracks the participant's status in the study. It will be completed at the last research visit (for participants who complete the study) or at the Early Termination Visit (for participants who discontinue study participation early). For participants who do not complete a final visit, the Study Completion form will be completed once the Visit 4 research visit window elapses. This form will be used in data analyses to address variables such as treatment retention and completion.

Protocol Deviations: Protocol Deviations will be assessed and documented throughout the study. This form will document a description of the deviation, how it occurred, the corrective action taken to resolve the specific deviation, as well as a description of the plan implemented to prevent future occurrences of similar deviations.

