4.4.4. Methadone Treatment Assessments

Methadone Visit Checklist: This form will be completed by the study pharmacists to document all study medication administered and dispensed at each Pharmacy visit, including the daily prescribed dose of methadone and the lot number and expiration date of administered/dispensed medication. This form also will be used to document pharmacist-provided care, such as (1) performing methadone prescription reconciliation, (2) providing patient education (e.g., safe storage, medication side effects); (3) checking and recording the patient's controlled medications prescription status using the NC Controlled Substances Reporting System [CSRS]; (4) monitoring and recording safety related events/concerns and communicating with the OTP medical physician or staff promptly regarding the event/concern; and (5) administering one methadone dose at the pharmacy and dispensing methadone according to the prescription of the OTP physician and applicable federal/state guideline for methadone treatment for opioid use disorder. Communications between the study pharmacist and the OTP medical physician or staff will be documented on the form, such as reasons for changes in methadone doses and/or take-home schedule.

Methadone Call-Back: The OTP medical staff (e.g., nurse) will implement the call back procedure. This form will collect the written results provided from the OTP medical staff to document the outcome of each random methadone call-back visit during the study period (i.e., at least once for every study participant after the first methadone dispensing by study pharmacist(s)), including the amount of used and unused medication returned. Failure to successfully complete call back result in termination from the study and return of the participant to the OTP for further assessment and ongoing treatment. This Methadone Call-Back form will include questions assessing whether a random methadone call-back visit is completed, its date, and the outcome of the call back (e.g., brought back all doses or not). The OTP staff is required to sign and date the form that a call back was done and its results (e.g., brought back all doses or not).

Treatment Satisfaction Survey: Participants, pharmacists and methadone treatment physicians will be asked to rate their overall satisfaction with the quality of the treatment (modified from Harland et al., 2015). Participant

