- **If illicit or non-prescribed opioid use is reported, found on drug testing, or suspected at any time during treatment**, the participant will be contacted to perform at least one random urine drug use test prior to the next scheduled visit and referred to the study physician for an assessment and to determine whether the participant should continue in the study.
- **Any non-prescribed use of benzodiazepines that is detected will prompt analogue measures to those adopted for opioid use**. The abuse of other substances or alcohol will result in early termination from the study and return to the OTP for methadone dosing and possible adjustment of the take home schedule.

Missing monthly research assessment visits and the rule for early study termination

- If the participant misses a scheduled monthly research assessment visit, alternative visits will be scheduled to collect the data.
- Missed visits will be documented using the Missed Visit Form. Remote/virtual interviews by phone or a Duke-approved teleconferencing platform for research may be used to collect study assessments for missed visits.

10. **Participant Discontinuation**

All participants will be followed for the duration of the study (approximately 3 months for pharmacy OUD maintenance) unless they withdraw consent, stop the methadone medication for OUD, die, or the investigator or sponsor decides to discontinue their enrollment for any reason. In addition to what is

described previously (discontinuation based on missed visits and/or illicit substance use), reasons for the investigator or sponsor to terminate a participant from the study may include, but are not limited to: study participation becoming unsafe, the participant becoming a threat to self or others, lack of funding, or early termination of the study for safety reasons. Of note, participants who discontinue methadone for any reason will be discontinued from the study.

- If a participant is discontinued from the study, an Early Termination Visit and End of Medication form should be completed as soon as possible following participant discontinuation to assess the participant's safety.

11. Description of what happens to participants receiving therapy when study ends or if a participant's participation in the study ends prematurely.

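### Section 13.2 measures retention as completed research assessments, so the proportion of participants staying in pharmacy treatment (objective c) has no place in the analysis plan

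*Combined protocol and SAP*

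**What the plan says.** Section 2, objective c, commits the pilot to examining "retention in treatment, as determined by the proportion of participants who remain in treatment at the pharmacy during the 3-month follow-up phase". The Abstract says that the secondary outcomes "will include recruitment rate, treatment retention, opioid and other substance use" and further items, without defining retention there. Section 4.4.1 says of the Study Completion form: "This form will be used in data analyses to address variables such as treatment retention and completion".

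Section 13.2 contains one retention item. Its heading joins treatment retention to the follow-up assessments, and its definition reads: "Retention in follow-up assessments is defined as the proportion of study assessments completed (three follow-up assessments".

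Two provisions separate those assessments from pharmacy attendance. Section 4.3 says: "These follow-up assessments will be completed either in-person between the participant and research staff or remotely via phone". Section 9 says that when a monthly assessment is missed, "alternative visits will be scheduled to collect the data".

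**The concern.** The unit and the event both change between Section 2 and Section 13.2. In objective c the unit is the participant and the event is leaving pharmacy dispensing. In 13.2 the unit is the assessment and the event is a missed interview.

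Section 13.3 plans descriptive analysis of the primary and secondary outcome measures. An outcome that 13.1 and 13.2 do not define therefore has no stated analysis, denominator or counting rule. An analyst working from Section 13 would report interview completion under a treatment-retention label.

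The pilot is meant to inform a randomised trial, and whether stable patients stay in pharmacy dispensing is one of its listed objectives. The background in Section 3.3 describes earlier US work in participant terms: none of 13 office-based patients left treatment. A completion rate for interviews cannot be set beside a figure of that kind.

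**Working it through.** The plan states no figure for retention, so there is nothing to reproduce. The check compares the texts and then illustrates how far the two measures can separate.

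**Does anything else in Section 13 supply objective c?**

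- Section 13.1 (adherence) concerns scheduled doses received out of methadone prescribed. It does not measure remaining at the pharmacy.
- The recruitment item in 13.2 includes the share of consented participants who reach the pharmacy phase. That is entry, not staying.
- Section 13.3 refers back to the listed outcomes and adds no definition.

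None of them does.

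**Inputs**

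- N = 20 participants, the upper limit in Section 4.1.
- Three follow-up assessments each (Section 13.2), so 3 × 20 = 60 in total.
- k = number who leave the pharmacy, and m = assessments each leaver completes. Both are assumptions.
- Completions are pooled over 60. Section 13.2 does not say whether it pools.

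**Formulas, when leavers are the only source of missed assessments**

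- Objective c: R = (N − k)/N
- Section 13.2: C = [3(N − k) + mk]/(3N)
- Difference: C − R = mk/(3N)

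| k | R | C at m = 0 | m = 1 | m = 2 | m = 3 |
|---|---|---|---|---|---|
| 2 | 90% | 90.0% | 93.3% | 96.7% | 100% |
| 4 | 80% | 80.0% | 86.7% | 93.3% | 100% |
| 6 | 70% | 70.0% | 80.0% | 90.0% | 100% |

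With any leavers, the two agree only when every leaver completed no assessment. Otherwise 13.2 gives the higher figure.

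**The opposite direction.** If all 20 stay and j of them each miss one assessment that is not made up, R = 100% and C = (60 − j)/60. This is 96.7%, 93.3% and 90.0% for j = 2, 4 and 6.

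**Same reported figure, different retention**

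- Case A: four leave after the Month 2 assessment. C = (16 × 3 + 4 × 2)/60 = 56/60 = 93.3%, and R = 16/20 = 80%. Section 13.2 is 13.3 points higher.
- Case B: all stay and four each miss one assessment. C = 56/60 = 93.3%, and R = 20/20 = 100%. Section 13.2 is 6.7 points lower.

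Per-participant reporting does not separate the cases. In both, 16 participants have 3/3 and 4 have 2/3, the mean is (16 × 1 + 4 × 2/3)/20 = 93.3%, and 16/20 complete all three.

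**The case against.** The best reply is that objective c has not been lost. Section 2 still defines it, the Abstract lists treatment retention, and Section 4.4.1 assigns the Study Completion form to its analysis. Section 13.2 is also brief elsewhere: its substance-use item names neither the urine screens nor the timeline followback. A team reading the whole document would probably report pharmacy retention anyway, and the defining sentence in 13.2 does say that it concerns follow-up assessments.

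A second reply is that leaving the pharmacy usually ends study participation too, so the measures will move together. On call-back, Section 4.4.4 says: "Failure to successfully complete call back result in termination from the study and return of the participant to the OTP". Section 15.2 says: "If the participant misses two consecutive visits, he/she will be discontinued from study". Stopping methadone (Section 10), overdose, pregnancy, prisoner status and suspected diversion also end participation.

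A third is that the size depends on chosen cases. With four leavers the gap could be 0, 6.7, 13.3 or 20 points, and Case B needs missed interviews that rescheduling and remote contact failed to recover.

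Much of this stands as a limit on size. The intent is visible, the data exist, the measures will be correlated, and the gap may be small. It does not remove the problem. For the substance-use item, 13.2 is merely less detailed; for retention it states a different quantity. Assessments completed before an exit still count towards 13.2 even when the exit ends participation. Section 9 also allows a return to routine OTP dispensing after an off-schedule pharmacy visit without saying that research follow-up then stops.

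**Conclusion.** The concern holds. Section 13.2 defines retention as a different quantity from the trial's own objective, attaches the treatment-retention label to it, and leaves the objective c proportion without a stated analysis. The 13.2 figure alone cannot recover that proportion: 93.3% completion is compatible with pharmacy retention of 80% or 100% in the two cases shown.

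Those sizes rest on assumed departures and missed interviews, full enrolment of 20, and pooling over 60. The documents give no expected retention rate. The trial is descriptive, with no hypothesis and no go/no-go rule based on retention, so no error rate or sample size is affected. What is at risk is a mislabelled feasibility result passed on to the design of the next trial. It should be corrected, but it does not threaten the study.

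**What to change.** In Section 13.2:

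1. Make objective c the treatment-retention outcome: the proportion of participants who remain in pharmacy treatment through the 3-month phase, reported as n/N. The Study Completion form, the End of Methadone Medication Form and the Methadone Visit Checklist are the sources.
2. State the denominator. Objective c says only participants, and eligibility is settled after consent, so those consented and those who start pharmacy dispensing may differ. Participants who start pharmacy dispensing are the natural choice for a measure of staying in it.
3. State how to count a participant who is sent to the OTP for one visit and then returns to pharmacy dispensing, which Section 9 lists as a possible outcome.
4. Keep assessment completion as a separate outcome under its own name, and say whether it is pooled over assessments or summarised per participant.

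A separate minor item affects the data source. Section 4.4.1 says that it follows Table 1's visit numbering, yet for participants without a final visit it completes the Study Completion form when the Visit 4 window closes. In Table 1, Visit 4 is Month 2 and Visit 5 is Month 3. Sections 4.4.2, 4.4.4 and 15.2 also number visits as though Visit 4 were the last. These should be reconciled with Table 1.

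The cost is wording only, since the forms already collect the data.
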